#### **4.2.2 Hazards/Harms**

This will be the first study to evaluate the use of ALNB in clinical practice; there is currently no direct clinical evidence concerning the safety of ALNB.

ALLEVYN LIFE has been used widely over the last four years and has been shown to be equivalent to ALNB with regard to materials and fluid handling properties (see Section 6).

Published clinical studies with ALLEVYN LIFE, risk management reports, and post-marketing

surveillance (PMS) data consistently indicate that the risk of adverse events is low and that reactions which do occur are generally local to the application site and are mild in severity. Adverse events are well characterized and are manageable in the majority of cases. As such, ALLEVYN LIFE demonstrates an acceptable benefit-risk profile.

Because of the similarities between ALLEVYN LIFE and ALNB, the anticipated medical benefits of ALNB are also expected to outweigh risks. There are some differences between the two products, including:

- ALNB can be cut to size without compromising its performance characteristics
- ALNB does not incorporate a change indicator, as this would be obscured by any secondary dressing
- ALNB includes a lower tack adhesive, to serve as a ‘third hand’, and enable the dressing to be removed and repositioned more easily
- ALNB requires the use of a secondary dressing to aid retention

The use of a lower tack adhesive with ALNB may positively impact safety by lowering the incidence and severity of skin stripping resulting from its use. Unlike ALLEVYN LIFE, ALNB requires a secondary dressing to aid retention. Choice of ancillary dressing, together with associated risks relating to this secondary device, will be carefully monitored during this study.

There are no anticipated Serious Adverse Device Effects (SADE) associated with the use of ALNB.

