### 9.2.3 Routine Dressing Changes

As ALNB has a maximum recommended wear time of 7 days, routine dressing changes will occur between scheduled Study visits 2, 3, and the End of Study Visit. The number of these visits will vary from subject to subject, based on clinical judgment. These visits will involve subjects

returning to an on-site visit. Dressings should not be given to study subjects; the dressing should only be changed by an HCP at a visit.

1. Question subjects regarding any changes in health or concomitant treatment.
2. Ask the subject to assess the comfort of wearing the dressing since the last visit (see Section 9.5.8).
3. Assess the movement of the dressing (see Section 9.5.9).
4. Remove the old dressing and inspect the ulcer. Complete an ulcer assessment (see Section 9.5.1).
5. Assess the level of pain experienced by the subject when the dressing is removed (see Section 9.5.6).
6. Assess the ease of dressing removal, leakage, and absorption under compression (see section 9.5.10).
7. If any adverse events or device deficiencies are observed or reported, they must be recorded as instructed in Section 12 (Adverse Events and Device Deficiencies).  
NOTE: Photograph the ulcer only if reporting an AE or DevD.
8. Redress the ulcer, if clinically indicated per the subject's randomization assignment:
  - For subjects allocated to the experimental group, apply ALNB as supplied for use in the study, cutting the dressing to size if required and securing with a suitable secondary dressing.
  - For subjects allocated to SC apply a suitable protective dressing, other than ALLEVYN LIFE/ALNB.
9. Record details of all dressings used for all subjects, (e.g. brand, size, etc.) as well as any treatment applied underneath the dressing, such as Durafiber or Intrasite gel.  
For subjects randomized to ALNB, record whether or not the dressing was cut to a smaller size.

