### Condition of peri-wound

- Normal
- Erythematous
- Edematous
- Eczematous
- Excoriated
- Macerated

- Indurated

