A Pilot Randomized Controlled Trial to Evaluate an Advanced Borderless Dressing (ALLEVYN™ LIFE Non-Bordered) in the Treatment of Chronic Ulcers	ST: 1005
	Version: 1.0, 27-Jul-2018
	Page: 7 of 27

[figure not shown]
2. Introduction

The following Statistical Analysis Plan (SAP) details the statistical considerations, including the data analysis methods, for the Study Protocol CT1603ALF. Related documents to this SAP are the Study Protocol, Case Report Form (CRF), and Tables, Figures and Listings (TFLs) Shells.

3. Study Design

This is a stratified, randomized, parallel group study. Subjects will be randomly assigned to ALLEVYN™ LIFE Non-Bordered (ALNB) or Standard Care (SC) respectively in a 5:3 ratio. Subjects will be stratified by ulcer type: diabetic foot ulcer (DFU), leg ulcer (LU) and pressure ulcer (PU). Participation in the study will last up to 12 weeks. Subjects will be required to make at least one visit per week to the research site. The primary clinical endpoint will be six (6) weeks from enrollment, with clinical data also collected at three (3) and twelve (12) week follow-up visits. Health care resource use data will be gathered and compared over the entire twelve week study period. Figure 3.1 below shows an overview of the study design and table 3.1 shows the planned visit schedule.

Figure 3.1 – Overview of Study Design

CONFIDENTIAL AND PROPRIETARY

This document contains information that is confidential and proprietary to Smith & Nephew PLC and Smith & Nephew, Inc. and is intended for use only by Smith & Nephew and its manufacturer. It shall not be reproduced or copied in whole or in part, nor shall the contents be disclosed by any means without prior written permission from Smith & Nephew, nor shall anyone make any use of it that is contrary to the expressed or implied wishes of Smith & Nephew.

Statistical Analysis Plan	 smith&nephew
A Pilot Randomized Controlled Trial to Evaluate an Advanced Borderless Dressing (ALLEVYN™ LIFE Non-Bordered) in the Treatment of Chronic Ulcers	Number: CT1603ALF ST: 1005 Version: 1.0, 27-Jul-2018 Page: 8 of 27

Table 3.1: Study Visit Schedule

Procedure	Key Visits			Other Visits	
	Visit 1 (Baseline)	Visit 2 (Day 21±3) and Visit 3 (Day 42±4)	End of Study Visit (Day 84±4)	Routine Dressing Changes	Treatment D/C (before end of study)
Informed Consent	√				
Demographics/Medical History	√				
Concomitant Medication	√	√	√	√	√
CWIS	√	√	√		√
Ulcer Assessment	√	√	√	√	√
ABI	√ ¹				
Verify Inclusion/Exclusion	√				

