5.3 Secondary Endpoints

Ulcer progression variables to be compared between groups at three, six, and twelve weeks including:

- Modified Bates-Jensen Wound Assessment Tool
 - Undermining
 - Necrotic tissue type
 - Necrotic tissue amount
 - Exudate type

CONFIDENTIAL AND PROPRIETARY

This document contains information that is confidential and proprietary to Smith & Nephew PLC and Smith & Nephew, Inc. and is intended for use only by Smith & Nephew and its manufacturer. It shall not be reproduced or copied in whole or in part, nor shall the contents be disclosed by any means without prior written permission from Smith & Nephew, nor shall anyone make any use of it that is contrary to the expressed or implied wishes of Smith & Nephew

Statistical Analysis Plan	
A Pilot Randomized Controlled Trial to Evaluate an Advanced Borderless Dressing (ALLEVYN™ LIFE Non-Bordered) in the Treatment of Chronic Ulcers	Number: CT1603ALF
	ST: 1005
	Version: 1.0, 27-Jul-2018
	Page: 11 of 27

- Exudate amount
- Skin color surrounding the wound
- Granulation tissue
- Epithelialization
- Condition of peri-wound
- Ulcer dimensions
- Ulcer healed status

Healthcare resource use variables (to be compared between groups over the entire twelve week study period) including:

- Dressings used (number and type for both primary and secondary dressings), including use of compression therapy
- Healthcare consultations (number and type)
- Time spent by health care providers (HCP) in treating/caring for reference ulcer
- Time in hospital (nights spent as an inpatient due to reference ulcer)
- Interventions/procedures related to the reference ulcer (number and type), including debridement of the ulcer (curette, scissors, scalpel, forceps, other)
- Concomitant therapies/treatments (number and type) used on the reference ulcer

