7.3 Handling of Missing or Incomplete Data

Cardiff Wound Impact Schedule (CWIS)

CONFIDENTIAL AND PROPRIETARY

This document contains information that is confidential and proprietary to Smith & Nephew PLC and Smith & Nephew, Inc. and is intended for use only by Smith & Nephew and its manufacturer. It shall not be reproduced or copied in whole or in part, nor shall the contents be disclosed by any means without prior written permission from Smith & Nephew, nor shall anyone make any use of it that is contrary to the expressed or implied wishes of Smith & Nephew

Statistical Analysis Plan	
A Pilot Randomized Controlled Trial to Evaluate an Advanced Borderless Dressing (ALLEVYN™ LIFE Non-Bordered) in the Treatment of Chronic Ulcers	Number: CT1603ALF
	ST: 1005
	Version: 1.0, 27-Jul-2018
	Page: 14 of 27

If a subject does not have any CWIS data for a post-baseline visit and has at least one post-baseline score then the Last Observation Carried Forward (LOCF) method will be used to carry forward the overall CWIS score.

If a subject is only missing part of the CWIS data at a post-baseline visit, whether that is a full domain or just part of a domain, and has at least one post-baseline score then the LOCF method will be used only for this portion of the CWIS data and the domain scores and overall CWIS score will be calculated again.

For both above instances if the missing data is at the baseline assessment or there are no post-baseline assessments to carry forward then the relevant score will be left as missing.

Modified Bates-Jensen Wound Assessment Tool

If a subject has missing data for the Modified Bates-Jensen Wound Assessment tool and has at least one post-baseline score then the missing data will be handled using the LOCF method. If the missing data is at the baseline assessment or there are no post-baseline assessments to carry forward then the relevant score will be left as missing.

Condition of peri-wound

If a subject has missing data for the condition of the peri-wound and has at least one post-baseline score then the missing data will be handled using the LOCF method. If the missing data is at the baseline assessment or there are no post-baseline assessments to carry forward then the relevant score will be left as missing.

Ulcer dimensions

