7.11 Analysis of Secondary Endpoints

Modified Bates- Jensen Wound Assessment Tool

Part of the assessment of ulcer progression will be done using a modified version of the Bates- Jensen Wound Assessment tool assessing: undermining, necrotic tissue type, necrotic tissue amount, exudate type, exudate amount, skin color surrounding the wound, granulation tissue and epithelialization. Each item will be scored according to section 9.5.1 of the study protocol. A total score for each subject at each assessment will be calculated by summing the scores for all 8 items.

The total score for the modified Bates- Jensen Wound Assessment tool will be summarized using descriptive statistics at all visits by treatment and overall. Repeated measures ANCOVA model will be used with the total score as the dependent variable. As a minimum the model will contain terms for treatment, visit and a treatment-by-visit interaction term. The following terms will be added to the model using a stepwise selection procedure with an F-value to attain a significance level of 0.1: centre, wound

CONFIDENTIAL AND PROPRIETARY

This document contains information that is confidential and proprietary to Smith & Nephew PLC and Smith & Nephew, Inc. and is intended for use only by Smith & Nephew and its manufacturer. It shall not be reproduced or copied in whole or in part, nor shall the contents be disclosed by any means without prior written permission from Smith & Nephew, nor shall anyone make any use of it that is contrary to the expressed or implied wishes of Smith & Nephew

Statistical Analysis Plan	
A Pilot Randomized Controlled Trial to Evaluate an Advanced Borderless Dressing (ALLEVYN™ LIFE Non-Bordered) in the Treatment of Chronic Ulcers	Number: CT1603ALF
	ST: 1005
	Version: 1.0, 27-Jul-2018
	Page: 23 of 27

type, BMI and baseline CWIS-PSDL score. The difference in least squares mean (LSMean) between treatments at the 3, 6 and 12 week visit will be presented with the associated 95% confidence interval.

Other assessments of ulcer progression

- Condition of peri-wound (categorized as Normal, Erythematous, Edematous, Eczematous, Excoriated, Macerated, Indurated) at each post-baseline time point cross-tabulated with condition of peri-wound at baseline.

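### Peri-wound condition is recorded at every dressing change but analysed only at weeks 3, 6 and 12, so the one planned table can miss skin reactions that settle between those visits

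*SAP*

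**What the plan says.** **Collection.** Protocol 9.5.1 includes "Condition of peri-wound" in the ulcer assessment, with seven unranked states: normal, erythematous, edematous, eczematous, excoriated, macerated and indurated. Protocol 9.2.3, step 4, applies that assessment at routine dressing changes: "Remove the old dressing and inspect the ulcer. Complete an ulcer assessment (see Section 9.5.1". SAP Table 3.1 ticks ulcer assessment for routine dressing changes and for the treatment-discontinuation visit. On frequency, SAP section 3 states: "Subjects will be required to make at least one visit per week to the research site". Protocol 9.2.3 adds: "As ALNB has a maximum recommended wear time of 7 days, routine dressing changes will occur between scheduled Study visits".

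**Analysis.** SAP 7.11 tabulates peri-wound condition "at each post-baseline time point cross-tabulated with condition of peri-wound at baseline" and lists no weeks in that sentence. The weeks come from SAP 5.3, whose list contains peri-wound condition: "Ulcer progression variables to be compared between groups at three, six, and twelve weeks including". Protocol 10.2.2.2 sets the same three times.

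**Missing values.** SAP 7.3: "If a subject has missing data for the condition of the peri-wound and has at least one post-baseline score then" the last observation is carried forward. It does not say whether a value from a routine or discontinuation visit may be the one carried.

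**Expected harm.** Protocol 4.2.2, drawing on experience with ALLEVYN LIFE, says that "reactions which do occur are generally local to the application site and are mild in severity".

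**The concern.** The harm that the protocol expects is local and mild, which is what a peri-wound category can show. The measure uses the same categories in both arms and needs no causality judgement. It is collected at least weekly, yet the analysis reads it on three occasions.

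A state that appears after week 6 and clears before week 12, for example, leaves no trace in the cross-tabulation. A reaction that leads to stopping the dressing can be absent too. After discontinuation any continuing care is standard care (Protocol 9.2.6), and subjects already withdrawn from treatment need no full ulcer assessment at later visits (Protocol 9.2.4 and 9.2.5).

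At stake is the completeness of a descriptive safety picture in a pilot whose stated aims include safety data for post-market surveillance (Protocol section 5). The primary endpoint is not affected.

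**Working it through.** The plan gives no figure on this point, so there is none to reproduce.

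**Inputs from the documents**
- Tabulated times: days 21, 42 and 84 (SAP 5.3 and Table 3.1).
- Assessments: at least one a week, so at least 12 after baseline for a subject dressed throughout (SAP section 3).

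**Inputs assumed** (the documents give neither)
- Onset uniform over the 84 days.
- Reaction duration *d*, from 3 to 28 days.

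**Step 1. Share of assessments outside the table**
- One visit a week: (12 − 3)/12 = 75%.
- Two visits a week: (24 − 3)/24 = 87.5%.

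**Step 2. Chance that a reaction is present on a tabulated day**

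The gaps before the three tabulated days are 21, 21 and 42 days, so

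P(in table) = [min(*d*,21) + min(*d*,21) + min(*d*,42)] / 84.

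With weekly assessments the chance of being seen at all is min(*d*/7, 1).

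| Duration | In the table | Missed by the table | Seen at some weekly assessment |
|---|---|---|---|
| 3 days | 9/84 = 11% | 89% | 43% |
| 5 days | 15/84 = 18% | 82% | 71% |
| 7 days | 21/84 = 25% | 75% | 100% |
| 10 days | 30/84 = 36% | 64% | 100% |
| 14 days | 42/84 = 50% | 50% | 100% |
| 21 days | 63/84 = 75% | 25% | 100% |
| 28 days | 70/84 = 83% | 17% | 100% |

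A simulation of 2,000,000 onsets gave the same values to within rounding.

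**Step 3. Check by counting weeks**

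Take an onset week from 1 to 12 and count the onsets whose span includes week 3, 6 or 12.
- One weekly assessment long: weeks 3, 6, 12, so 3/12 = 25%.
- Two long: weeks 2, 3, 5, 6, 11, 12, so 6/12 = 50%.
- Three long: weeks 1 to 6 and 10 to 12, so 9/12 = 75%.

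**Step 4. What this means in a small arm**

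Suppose five subjects each have one independent seven-day reaction (an assumed count). The expected number in the table is 5 × 0.25 = 1.25, and the chance that none appears is 0.75^5 = 24%. With three such subjects it is 0.75^3 = 42%.

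**Step 5. Direction of the carry-forward rule**

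The discontinuation visit includes an ulcer assessment (Protocol 9.2.6, step 5). If its value may be carried forward, a reaction that ended treatment is repeated at later weeks and over-represented. If only key-visit values are carried, an older value stands in its place. SAP 7.3 fits both readings, so no direction follows.

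**The case against.** **Adverse events are a separate route.** Protocol 12.1.1 defines an adverse event broadly enough to include a new unfavorable sign, whether or not related to the device. Events are recorded at every routine dressing change, with a photograph of the ulcer (Protocol 9.2.3), and treatments for peri-ulcer erythema, irritation or itching are captured (Protocol 9.2.8.2). SAP 7.13 counts subjects with adverse events and compares device-related events by Fisher's exact test. This stands: a reader who infers that brief reactions go unreported altogether goes too far. But no rule links a new peri-wound state to an adverse event, so capture depends on site judgement in an open-label trial. SAP 7.13 also words its system organ class and preferred term tables for treatment-related events, where Protocol 10.3 says treatment-emergent.

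**Peri-wound condition is not a safety endpoint, nor the only skin measure.** Correct. It is listed under ulcer progression, and the modified Bates-Jensen tool scores surrounding skin color from 1 to 5. SAP 7.11, however, analyses only the eight-item Bates-Jensen total, in which a color change is not separately visible.

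**Skin stripping.** A reader might infer that the table should test the protocol's remark that the lower-tack adhesive may reduce skin stripping. The remark compares ALNB with ALLEVYN LIFE (Protocol 4.2.2), and standard care excludes ALLEVYN variants (Protocol 6.1.2). No table in this trial could test it.

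**Fixed visits give equal ascertainment.** This also stands. Counting any occurrence gives the arm with more dressing changes more chances to record a state. That is a reason to keep the fixed-visit table and to show the number of assessments beside the new one.

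**The 7.11 sentence is open.** It could be read as covering every visit. SAP 5.3 and Protocol 10.2.2.2 make weeks 3, 6 and 12 the better reading, and routine visits fall at subject-specific times that give no common point for a cross-tabulation.

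**Conclusion.** The point holds as a gap in a descriptive analysis. Peri-wound condition is collected at least weekly, its analysis is set at three visits, and no any-occurrence summary is planned. Under uniform onset and weekly assessment, the cross-tabulation would miss about 75% of one-week, 50% of two-week and 25% of three-week reactions. It misses most reactions only when they last less than 14 days, and the documents do not say how long they last.

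Two stronger readings are not supported. The loss concerns this one table, because a reaction may still be counted as an adverse event. And the carry-forward rule cannot be said to cause under-reporting, because its source visits are undefined and it could act either way. The omission comes from the three-visit schedule. For a pilot sized on feasibility this is a low-cost improvement that is worth making; it is not a flaw in the main comparison.

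**What to change.** 1. In SAP 7.11 or 7.13 add one descriptive table by treatment group in the Safety Population: number and percentage of subjects with any abnormal peri-wound category not present at baseline, for each category and for any. Use all observed assessments while on the allocated dressing, including the treatment-discontinuation visit, without LOCF. Define the event as a new category; the seven states have no order, so a worsening criterion would need a ranking that the protocol does not give.
2. Beside it show the number of assessments per subject and the proportion of assessments with a new abnormal category, by arm.
3. Keep the existing cross-tabulation and name weeks 3, 6 and 12 in SAP 7.11.
4. State in SAP 7.3 which visits may supply a carried-forward peri-wound value.

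The cost is one table and two clarifying sentences. The data are already collected and no clinical procedure changes. The drawback is unequal numbers of assessments between arms. Item 2 makes this visible but does not remove it, so the table should stay descriptive, without a test.

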## **2. SYNOPSIS**

---

Financial Disclosure Information for U.S. FDA Submission  
to be Obtained?

Yes       X No

---

Investigational Products:      ALLEVYN LIFE Non-Bordered

Product Used in Study:      ALLEVYN LIFE Non-Bordered is a borderless, multilayer foam dressing with a silicone adhesive.

Active Ingredients:      NA

---

Objective(s):      The primary objective is to estimate the effect of treatment with Allevyn Life Non-Bordered (ALNB) on Health-Related Quality of Life (HRQoL) in subjects with chronic ulcers, measured using the Cardiff Wound Impact Schedule Physical Symptoms and Daily Living (CWIS-PSDL) scale, compared to subjects receiving SC alone, over a six week treatment period.

Secondary objectives of this study are:

- 1) To estimate the effects of treatment with ALNB, when compared with SC alone, on:
  - a. HRQoL measured by the CWIS-PSDL scale at three and twelve weeks, and CWIS well-being (WB), social life (SL); global quality of life (GQ); and satisfaction with quality of

life (SQ) scales; at three, six, and twelve weeks

- b. Ulcer progression (including undermining, necrotic tissue type and amount, exudate type and amount, skin color surrounding the wound, granulation tissue, epithelialization, condition of peri-wound, ulcer dimensions and healing status) at three, six, and twelve weeks
- 2) Health care resource use related to the reference ulcer (including number and cost of dressings used, time in hospital, number and cost of additional treatments, procedures, and investigations) over twelve weeks

The exploratory objectives of this study are to compare differences between ALNB and SC in dressing performance (including wear time, leakage, odor control, and absorption under compression) and usability (including comfort and ease of application/removal together with associated pain) at three, six, and twelve weeks.

Study Population:

Adults aged 18 years and older with moderate to highly exuding chronic ulcers.

Structure: Parallel Group

Duration of Treatment: Up to 12 weeks

Duration of Assessment: Up to 12 weeks

Multi-Center:  Yes Number of Centers: Up to 6  
 No

Blinding:	 None	 Subject-Blind
		 Double-Blind

Randomization:	X	Yes	Group Assignment Ratio: 5:3 in favor of ALNB (ALNB n = 25; SC n = 15)
		No	Stratified by wound type: diabetic foot ulcer (DFU), leg ulcer (LU) and pressure ulcer (PU).

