6.1 Determination of Sample Size

Since there is no previous data upon which to base a sample size calculation, no statistical justification for the sample size is provided. Twenty-five (25) subjects were desired for the ALNB group; a 5:3 randomization ratio was selected so that approximately forty (40) subjects would be enrolled into the study. This number of subjects is based on feasibility only.

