- Ulcer length/width/depth will be used to derive area and volume. These variables will then be used to derive the reduction in area, depth, and volume from baseline to three, six and twelve weeks. The reduction in each dimension at each assessment (3, 6 and 12 weeks) will be analysed as the dependent variable in separate ANCOVA models. As a minimum the models will contain a term for treatment. The following terms will be added to the model using a stepwise selection procedure with an F-value to attain a significance level of 0.1: centre, subject, wound type, BMI and the relevant baseline wound dimension (area/ depth/ volume). The estimate difference in the LSMean reductions from baseline in area, depth, and volume (separately) between treatments will be presented with the associated 95% confidence interval.
- Reference ulcer healed (100% re-epithelialized, no drainage, no need for a dressing) will be summarized at each assessment (at three, six, and twelve weeks) and analyzed using a repeated measures logistic regression model with whether the reference ulcer was healed or not at the assessment as the dependent variable. As a minimum the model will contain a term for treatment. The following terms will be added to the model using a stepwise selection procedure with an F-value to attain a significance level of 0.1: centre, wound type and BMI..

Healthcare resource use

CONFIDENTIAL AND PROPRIETARY

This document contains information that is confidential and proprietary to Smith & Nephew PLC and Smith & Nephew, Inc. and is intended for use only by Smith & Nephew and its manufacturer. It shall not be reproduced or copied in whole or in part, nor shall the contents be disclosed by any means without prior written permission from Smith & Nephew, nor shall anyone make any use of it that is contrary to the expressed or implied wishes of Smith & Nephew

Statistical Analysis Plan	
A Pilot Randomized Controlled Trial to Evaluate an Advanced Borderless Dressing (ALLEVYN™ LIFE Non-Bordered) in the Treatment of Chronic Ulcers	Number: CT1603ALF
	ST: 1005
	Version: 1.0, 27-Jul-2018
	Page: 24 of 27

The following Healthcare resource variables will be summarized by treatment groups and overall (i.e. all assessments together) using continuous or categorical data summaries (as appropriate):

- Number and type of dressings used (both primary and secondary dressings), including use of compression therapy
- Number of outpatient visits

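### Healed-ulcer model: stepwise entry of centre in about 40 subjects is unreliable if a centre has no healed ulcer, and no treatment effect with a confidence interval is requested

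*SAP*

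**What the plan says.** SAP 7.11 (Analysis of Secondary Endpoints, reference ulcer healed) has healed status summarised at weeks 3, 6 and 12 and then "analyzed using a repeated measures logistic regression model with whether the reference ulcer was healed or not at the assessment as the dependent variable".

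- **Forced term.** "As a minimum the model will contain a term for treatment". No visit term and no treatment-by-visit term is named.
- **Candidate terms.** The rest enter "using a stepwise selection procedure with an F-value to attain a significance level of 0.1: centre, wound type and BMI".
- **Size.** SAP 6.1 expects that "approximately forty (40) subjects would be enrolled into the study". The protocol synopsis splits them 25 ALNB and 15 SC and gives "Number of Centers: Up to 6". Randomisation is stratified by ulcer type, not by centre (SAP 6.2).
- **Missing status.** It counts as not healed unless the ulcer was healed at the previous assessment (SAP 7.3).

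The SAP names no estimation method for this model. It gives no rule for separation, non-convergence or small centres. Its one fallback, Rank ANCOVA in SAP 7.9, belongs to the CWIS analysis. The Bates-Jensen and ulcer-dimension models in SAP 7.11 each ask for a treatment difference with a 95% confidence interval; the healed model does not.

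Protocol 10.2.2.2 planned a separate logistic model at each assessment. The move to one repeated measures model is not listed in SAP 7.15.

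**The concern.** Healing is a yes/no outcome that may be rare over 12 weeks. Six centres use five parameters, and 40/6 gives fewer than seven subjects per centre on average. If a centre has no healed ulcer at any visit, its coefficient runs off to minus infinity, whether the model is fitted by GEE or by maximum likelihood. In a logistic model an F-value for entry is in practice a Wald-type statistic, and Wald statistics behave badly in exactly this situation. Whether centre enters would then depend on which variance estimate the programmer happens to use, a choice the SAP leaves open.

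At stake are the reproducibility of one secondary analysis and the healing estimate that a pilot should hand on to the planning of a larger trial. Without a rule, the remedy would be chosen after unblinded data had been seen.

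**Working it through.** **Inputs from the documents:** 25 ALNB and 15 SC; up to 6 centres; 3 wound types with minimum sizes 5 + 3 = 8 each (Protocol 7.1); entry level 0.1; visits at weeks 3, 6 and 12.

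**Assumptions, because the documents give no figure:** healing by week 12 of 10% to 50%, equal in both arms and all centres; centre sizes as listed below.

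**1. The plan's own figure.** 25 × 8/5 = 40, so SC = 15. This reproduces.

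**2. Chance that at least one centre has no healed ulcer.** With p healed by week 12 and n_j subjects in centre j:

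P = 1 − ∏ [1 − (1 − p)^n_j]

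Example, sizes 7,7,7,7,6,6 and p = 0.30: 0.7^7 = 0.0824 and 0.7^6 = 0.1176, so P = 1 − 0.9176^4 × 0.8824^2 = 0.45.

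| Centres | 10% | 20% | 30% | 40% | 50% | P = 50% at p of about |
|---|---|---|---|---|---|---|
| 6 even (7,7,7,7,6,6) | 98% | 79% | 45% | 19% | 6% | 28% |
| 6 uneven (14,10,7,4,3,2) | 99.5% | 93% | 77% | 58% | 39% | 44% |
| 4 even (10 each) | 82% | 37% | 11% | 2% | 0.4% | 17% |
| 4 uneven (18,12,6,4) | 90% | 60% | 34% | 17% | 8% | 24% |

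**3. The entry test for centre.** 1,500 simulated trials per case, with no true centre or treatment effect, three visits per subject, and healing at weeks 3 and 6 set at 15% and 45% of the week-12 rate. Centre was tested at 0.1 after treatment. A sound test would admit it in about 10% of trials. Six even centres:

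| Test | 10% | 20% | 30% | 40% | 50% |
|---|---|---|---|---|---|
| Wald F, robust variance | 97% | 75% | 46% | 26% | 20% |
| Wald F, naive variance | 0.2% | 3% | 9% | 16% | 23% |
| Robust score test | 0% | 2% | 6% | 8% | 10% |

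The robust Wald result mostly tracks whether a centre is empty. At 20% healing it admits centre in 96% of trials with an empty centre and 2.7% of the others. The reason is that as the coefficient grows, the robust standard error stays bounded, so the statistic grows too. The naive standard error grows faster than the coefficient, so that statistic shrinks.

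**4. The treatment coefficient.** With treatment alone in the model, it diverges only if an arm has no healed ulcer at any visit:

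P = (1 − p)^25 + (1 − p)^15 − (1 − p)^40

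At p = 0.10 this is 0.072 + 0.206 − 0.015 = 26%. At 20/30/40% it is 3.9/0.5/0.05%.

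With centre and wound type both forced in (assumed centre shares 0.30/0.25/0.15/0.12/0.10/0.08), two sets of simulated trials gave a diverging treatment coefficient in 33/5/2/0% and about 35/6/1/0% at 10/20/30/40% healing.

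**5. What remains if only centre is dropped.** P(no healed ulcer among 15 SC) = (1 − p)^15 = 21/3.5/0.5% at 10/20/30%. P(a wound type with none healed) is 70/31/11% for sizes 8, 8, 24 and 57/15/2.6% for sizes 14, 13, 13. Some sparse-data protection is still needed when healing is low.

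**The case against.** The strongest defence is that the result of interest is the treatment effect, and that mostly survives. Centre is only a candidate. A centre with no healed ulcer carries no information on treatment, so the other centres still estimate it. Step 4 bears this out from about 20% healing upward. The healing rate and centre sizes are assumed, and up to six centres could mean three or four. Healed status is also summarised at each visit whatever the model does, and SAP 7.1 allows for 95% intervals where appropriate. The trial is a pilot sized on feasibility, without multiplicity control, and Protocol 5.6 expects no significant differences.

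All of that stands as a limit on the consequences. It does not rescue the entry rule, whose behaviour depends on an unstated variance choice, and it does not supply the missing effect measure.

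A reader might infer more than the documents support:

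- **That the treatment odds ratio will usually be non-estimable.** Step 4 shows otherwise unless healing is near 10%. Divergence of some coefficient, mostly a centre term, is not divergence of treatment.
- **That an arm with no healed ulcer at week 3 breaks the SAP model.** It would break a separate week-3 model or a treatment-by-visit contrast. The SAP model names neither.
- **That even a correctly specified model diverges in so small a trial.** The treatment-only model fails in 0.5% of trials at 30% healing.
- **That the F-test has no valid value.** It can be computed but is miscalibrated, and a score test stays computable.

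**Conclusion.** The point holds in a conditional form. With six centres, a centre without a healed ulcer is more likely than not if 12-week healing is below about 28% (even centres) or 44% (the uneven layout). It is unlikely with few even centres or common healing. When it happens, the F-value rule at 0.1 can be far too liberal or far too strict depending on the variance used: 75% against 3% entry of a null centre term at 20% healing with six even centres. The risk to the treatment odds ratio itself is about one trial in three at 10% healing, 5 to 6% at 20%, and 2% or less from 30%, even with centre and wound type forced in.

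The absence of a requested treatment effect with a confidence interval needs no assumption; it follows from the text of SAP 7.11. The effect is confined to one secondary endpoint and does not touch the primary analysis. The change is worth making because it is cheap and can be made before the data are seen.

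**What to change.** In the healed bullet of SAP 7.11:

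1. Delete the stepwise step and the centre and BMI candidates.
2. Pre-specify treatment and wound type, the randomisation stratum, and fit them by Firth-penalised logistic regression. Fitting each visit separately follows Protocol 10.2.2.2 and avoids combining the penalty with repeated measures. An empty arm can then occur at an early visit, but the penalised estimate stays finite.
3. Report the ALNB − SC difference in proportion healed at 3, 6 and 12 weeks with a Newcombe or Miettinen-Nurminen 95% confidence interval. Both remain defined when an arm has no healed ulcer. This difference is not adjusted for wound type; the Firth odds ratio is.
4. List the model change in SAP 7.15 if the final SAP still differs from the protocol.

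A Kaplan-Meier estimate of time to healing is optional. It needs no new data, because Protocol 9.2.3 already has the ulcer assessed at each routine dressing change and Protocol 9.5.1 includes healing status.

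The cost is SAP wording only, with methods standard in SAS 9.4. The downside is that there is no centre adjustment, which data this sparse could support only if healing is common or centres are few.
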